[figure not shown]
[figure not shown]

Title: Predicting Pain Response to Transcranial Direct Current Stimulation for Phantom Limb Pain in Limb Amputees.

Protocol: 2015P002525

Date: 06/06/2017

[figure not shown]
II. SPECIFIC AIMS

The specific aims of this experiment are as follows:

Aim 1: To assess the predictors of response to transcranial direct current stimulation (tDCS) in phantom limb pain of subjects with limb amputation. We will explore the aim 1 in an open-label pilot study in which patients will receive active tDCS during 5 daily sessions.

The primary endpoint will evaluate the predictors of pain response to tDCS measured by changes in PLP as indexed by a Visual Analog Scale. The study will require a total of 4 weeks to be completed. The first week, each patient will give daily reports of their pain using a VAS,

accounting for their PLP experience in the past 24hs. This initial baseline week will be followed by five days of treatment and a final 2-week follow-up period without any treatment to examine the lasting effects of the therapy. We will examine whether the following predictors are associated with treatment response: lower or upper limb, bilateral or unilateral and traumatic or non-traumatic amputation, baseline pain, age and gender by building a multivariate model.

IV. SUBJECT SELECTION

In this pilot study, we will recruit 50 subjects with phantom limb pain (PLP) of any etiology (traumatic, vascular disease, diabetic amputees or others). Subjects will need to meet all of the following inclusion criteria and none of the following exclusion criteria:

Inclusion Criteria:

1. Able to provide informed consent to participate in the study.
2. Subject is older than 18 years.
3. 3 months of phantom limb pain (experienced regularly for at least once a week) after the amputated limb has completely healed.*
4. Average pain of at least 4 on a numeric rating scale in the previous week (NRS; ranging from 0 to 10).
5. If the subject is taking any medications, dosages must be stable for at least 2 weeks prior to the enrollment of the study.

*The healing status of the limb will need to be confirmed by the subject's physician or by the physician of the protocol [name] (Co-Investigator).

Exclusion Criteria:

[figure not shown]
1. Pregnancy or trying to become pregnant in the next 2 months.
2. History of alcohol or drug abuse within the past 6 months as self-reported.

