3. Presence of the following contraindication to transcranial direct current stimulation

✓ Ferromagnetic metal in the head (e.g., plates or pins, bullets, shrapnel)

✓ Implanted head electronic medical devices (e.g., cochlear implants)

4. Head injury resulting in loss of consciousness for at least 30 min or post-traumatic amnesia for greater than 24 hours, as self-reported

5. Unstable medical conditions (e.g. uncontrolled diabetes, uncompensated cardiac issues, heart failure or chronic obstructive pulmonary disease).
6. Uncontrolled epilepsy, as defined by previous clinical seizure in the past 3 months in patients with treatment for epilepsy.
7. Suffering from severe depression (as defined by a score of >30 in the Beck Depression Inventory).*
8. History of unexplained fainting spells or loss of consciousness as self-reported during the last 2 years.
9. History of neurosurgery, as self-reported.

Description of interventions

tDCS Stimulation Protocol:

We will use Soterix Medical 1×1 tDCS stimulators device (© Soterix Medical Inc.), its sends a low-level current from the positive electrode, anode, to the negative electrode, cathode. During tDCS, low amplitude direct currents are applied via scalp electrodes and penetrate the skull to enter the brain. Direct current will be transferred by a saline-soaked pair of surface sponge electrodes (35 cm²) and delivered by a specially developed, battery-driven, constant current

stimulator with a maximum output of 10 mA. Subjects will receive daily stimulation sessions with active anodal tDCS for 5 days. Subjects are allowed to reschedule up to 1 stimulation visit. During each session, an anodal electrode will be placed over the primary motor cortex (M1), contralateral to the most painful amputation side and the cathode over the contralateral supraorbital area. Two milliamps of tDCS will be applied for 20 minutes [14].

DESCRIPTION OF ASSESSMENTS:

The following tests will be administered:

Visual Analogue Scale (VAS) for Pain: The VAS is a common assessment used which asks subjects to self-reportedly measure their pain on a visual scale (i.e., unbearable to none). We will use a VAS to determine subjects' pain scores. Subjects will rate their pain from 0 – indicating no pain at all, to 10 – indicating the worst pain felt. This scale is also colored, from green (at 0) to red (at 10), as a visual indicator of pain. This assessment tool is frequently used in many research studies evaluating pain levels [15, 19, 20].

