
Visual Analogue Scale (VAS) for Stump Pain: any painful sensation in the stump. Subjects will rate their stump pain from 0 – indicating no pain at all, to 10 – indicating the worst pain felt. The scale will include colors to help in identifying the correct response [15].

Visual Analog Scale (VAS) for Phantom Limb Sensation: all non-painful sensations in the amputated part of the limb. Subjects will be presented with a scale starting at 0- No phantom limb sensation, to 10 – Full sensation of the amputated limb. The scale will include colors to help in identifying the correct response [15].

Visual Analog Scale (VAS) for Phantom Limb telescoping: refers to the shrinking and retraction of the phantom towards the residual limb. Subjects will be presented with a scale starting at 0 - indicated that the phantom was enlarged, and 10 meant that the phantom was completely retracted into the stump the scale will include colors to help in identifying the correct response [15].

Adapted Groningen Questionnaire after Arm Amputation: This questionnaire will be applied to obtain information's concerning complaints that may be developed after arm amputation and has been used in several clinical trials assessing PLP [21].

Adapted Groningen Questionnaire after Leg Amputation: This questionnaire is originally meant to obtain information's concerning complaints that may be developed after arm amputation. We adapted the current arm version for lower limb amputation. This questionnaire [21] has been used in several clinical trials assessing PLP.

Pain and medication diary: To help monitor pain levels and medication use information, as well as safety. Subjects will be asked to record the number of phantom limb episodes on a daily basis, using a pain diary. They will record the intensity of the strongest episode as well as phantom limb sensation and stump pain on a colored visual analog scale included in the diary, where 0 represents no pain at all and 10 represents the highest pain the patient has ever felt. Moreover subjects will record their current medications and dosages daily in a pain medication diary, until completion of the study.

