For aim 1: The primary outcome is PLP indexed by VAS. PLP will be analyzed using changes in pain. To analyze these data, we will build a multivariate linear regression model in which the dependent variable will be the Visual Analogue Scale (VAS) for PLP using the following covariates: baseline pain (VAS), amputated limb (upper/lower), etiology of amputation (traumatic/ non traumatic), laterality of amputation (unilateral/bilateral), age, and gender. The first step will be perform a univariate analysis for each one of our predictors using univariate linear regression and obtain the values for the unadjusted b coefficients and 95% confidence intervals (CIs). After that, predictors associated with the outcome at a p level <0.01 will be used to build a multivariate linear regression using a forward stepwise model.

Additional statistical models for secondary outcomes will be developed in an exploratory manner. Therefore, we will not correct P values for multiple comparisons.

References

1. Flor, H., Phantom-limb pain: characteristics, causes, and treatment. *Lancet Neurol*, 2002. 1(3): p. 182-9.
2. Nikolajsen, L. and T. Staehelin Jensen, Phantom limb pain. *Curr Rev Pain*, 2000. 4(2): p. 166-70.
3. Manchikanti, L. and V. Singh, Managing phantom pain. *Pain Physician*, 2004. 7(3): p. 365-75.
4. Birbaumer, N., et al., Effects of regional anesthesia on phantom limb pain are mirrored in changes in cortical reorganization. *J Neurosci*, 1997. 17(14): p. 5503-8.
5. Borsook, D., et al., Acute plasticity in the human somatosensory cortex following amputation. *Neuroreport*, 1998. 9(6): p. 1013-7.
6. Flor, H., et al., Phantom-limb pain as a perceptual correlate of cortical reorganization following arm amputation. *Nature*, 1995. 375(6531): p. 482-4.
7. Grusser, S.M., et al., The relationship of perceptual phenomena and cortical reorganization in upper extremity amputees. *Neuroscience*, 2001. 102(2): p. 263-72.

8. Montoya, P., et al., The cortical somatotopic map and phantom phenomena in subjects with congenital limb atrophy and traumatic amputees with phantom limb pain. *Eur J Neurosci*, 1998. 10(3): p. 1095-102.
9. Ramachandran, V.S., D. Rogers-Ramachandran, and M. Stewart, Perceptual correlates of massive cortical reorganization. *Science*, 1992. 258(5085): p. 1159-60.
10. Davis, K.D., et al., Event-related fMRI of pain: entering a new era in imaging pain. *Neuroreport*, 1998. 9(13): p. 3019-23.

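### The pain scales have conflicting top anchors and the outcome scale is not named; if the diary, anchored to the patient's own worst pain, supplies the scores, predictor coefficients can be biased

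*Combined protocol and SAP*

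**What the plan says.** Three descriptions of the top of the scale appear under Description of Assessments.

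- **Pain and medication diary:** "0 represents no pain at all and 10 represents the highest pain the patient has ever felt". On this scale, "They will record the intensity of the strongest episode as well as phantom limb sensation and stump pain on a colored visual analog scale".
- **VAS for Pain, rating instruction:** "Subjects will rate their pain from 0 – indicating no pain at all, to 10 – indicating the worst pain felt". It does not say whose worst pain, or over what period. The VAS for Stump Pain uses the same wording.
- **VAS for Pain, opening sentence:** subjects "measure their pain on a visual scale (i.e., unbearable to none". This end point is not tied to pain history.

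Under Specific Aims, "The first week, each patient will give daily reports of their pain using a VAS", covering the past 24 hours. Under Statistical Analysis, "The primary outcome is PLP indexed by VAS. PLP will be analyzed using changes in pain". The covariates are "baseline pain (VAS), amputated limb (upper/lower), etiology of amputation (traumatic/ non traumatic), laterality of amputation (unilateral/bilateral), age, and gender". Each is first tested alone, and only those with p<0.01 go forward to a forward stepwise model. Baseline pain is not exempt from that screen. No variable for pain history or worst-ever pain is listed.

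**The concern.** A top anchor set by the patient's own history makes one point equal to a tenth of that patient's worst experience. For change within one patient this does no harm. Aim 1, however, regresses change on characteristics that differ between patients. If one group has a more severe personal maximum, the same true relief is recorded there as fewer points, and the instrument itself can create or hide a predictor effect. The plan says the results are to inform the design of a randomized trial, so such an effect could be carried forward.

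Whether this applies depends first on which form supplies the scores. The diary is the only daily pain form described, so it may be the source of the baseline-week reports. The plan does not say so. It also leaves open that baseline could come from one anchor and follow-up from another.

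**Working it through.** **The plan's own figure.** The plan gives no figure on the scales. Its sample size, 5 variables x 10 subjects = 50, reproduces and does not depend on the anchor.

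**Algebra.** Let L be pain on a common scale and A the patient's own worst pain on that scale. The recorded score is b = 10 x L/A.

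- Equal absolute relief d: recorded fall = 10 x d/A. It depends on A even among patients with the same b.
- Proportional relief p: recorded fall = 10 x p x L/A = p x b. Once b is known, A no longer matters.
- Percent change: (fall in b)/b. The factor 10/A cancels for each patient.

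Baseline adjustment therefore repairs the second case and not the first.

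**Size by arithmetic.** Let k be the ratio of worst-ever pain between two groups (assumed). For a mean fall of 2 points (assumed), the spurious difference is 2 x (1 - 1/k):

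- k = 1.1: 2 x 0.091 = 0.18
- k = 1.25: 2 x 0.20 = 0.40
- k = 1.5: 2 x 0.333 = 0.67

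**Simulation 1.** N = 50, 1,500 trials per setting, no true etiology difference in response. All inputs except N are assumed: even etiology split, mean pain 6 (SD 1.5), mean fall 2 points or 33%, SD of change 1.5, within-group log-SD of the anchor 0.10. The entry threshold of 4 is applied to the recorded score; the plan's criterion is on a numeric rating scale. The table shows relief under-recorded in the group with the higher worst-ever pain, in points.

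| k | Equal absolute fall: unadjusted | Baseline-adjusted | Equal proportional fall: unadjusted | Baseline-adjusted |
|---|---|---|---|---|
| 1.0 | -0.01 | -0.01 | 0.00 | 0.00 |
| 1.1 | 0.19 | 0.16 | 0.13 | -0.02 |
| 1.25 | 0.37 | 0.32 | 0.30 | -0.01 |
| 1.5 | 0.63 | 0.54 | 0.47 | -0.02 |

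Chance of passing the univariate p<0.01 screen, for k = 1.0 / 1.1 / 1.25 / 1.5:

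- Etiology, falsely: 1.3 / 1.4 / 4.8 / 11.8% under absolute relief; 1.5 / 1.5 / 2.5 / 5.1% under proportional relief.
- Baseline VAS: 1.7 / 2.2 / 3.2 / 7.7% under absolute relief; 31.4 / 29.7 / 31.8 / 40.2% under proportional relief.

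So where adjustment would remove the artefact, the screen lets baseline through in only about 30 to 40% of trials.

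**Simulation 2.** 25 against 25 patients, 4,000 trials per k, equal absolute relief. Assumed: true pain mean 6.5 (SD 1.5), true relief mean 2.3 (SD 2.0), recorded entry score 4 to 10, floor at 0.

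- Relief under-recorded at k = 1.1 / 1.25 / 1.5: 0.22 / 0.45 / 0.75 points. A repeat that also fitted baseline gave 0.20 / 0.45 / 0.73 unadjusted and 0.19 / 0.42 / 0.68 adjusted.
- False selection at p<0.01 on point change: 2.0 / 4.7 / 15.5%, against 0.8% at k = 1.
- False selection at p<0.01 on percent change: 0.9 / 1.2 / 2.2%, against 0.8% at k = 1.

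**The case against.** The strongest reply is that the personal anchor has not been shown to reach the primary analysis. Only the diary wording is explicitly personal, and the diary's stated purpose is to help monitor pain, medication use and safety. The VAS for Pain carries no lifetime qualifier and is also described by a history-free end point. A reader might infer that all the pain scales are anchored to the patient's own past. The text does not support that: the VAS for Pain is ambiguous, and the source of the outcome is unstated. This part of the reply stands, and it is why the point is conditional.

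A second reply is that nothing in the documents says worst-ever pain differs by etiology, age or gender. That also stands. The ratio k is an assumption throughout, and even its direction is unknown.

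A third is that baseline VAS is a listed covariate and removes the artefact when relief is proportional. That is correct, but it covers only one response model. The plan does not guarantee that baseline stays in the model, and the unadjusted coefficients and intervals from the univariate step would still carry the bias.

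Finally, the plan presents itself as exploratory and hypothesis-generating. That lowers the severity, but it does not make conflicting anchors harmless or costly to reconcile.

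**Conclusion.** The anchors conflict, and the plan should name the scale that supplies the baseline and outcome PLP scores. That much follows from the text alone.

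The bias is conditional. It needs the personally anchored scale to supply the scores, and worst-ever pain to differ along a candidate predictor. Under both conditions and equal absolute relief, the coefficient shifts by about 0.2 points at an assumed ratio of 1.1 and about 0.37 to 0.45 at 1.25. At 1.1, false selection barely rises above its level with a common anchor. The larger rates at 1.5 rest on the most extreme ratio tried. Under proportional relief, the shift disappears once baseline VAS is in the model.

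A reader might go further and conclude that the etiology, age and gender coefficients do mix response with pain history. The documents do not establish that; they show only that the plan leaves the possibility open. Severity is minor.

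**What to change.** 1. Put one identical top anchor that does not refer to the patient's own history, for example 'worst pain imaginable', on the clinic PLP VAS and the diary, and remove the competing descriptions. State in Specific Aims and Statistical Analysis that this one scale supplies both baseline and outcome. Do not switch anchor within a patient's follow-up. This reduces dependence on pain history but may not remove it, because each respondent still sets the imagined maximum.
2. Keep baseline VAS in the multivariate model whatever its univariate p-value. This uses one model term.
3. As a sensitivity analysis, repeat the Aim 1 regression with percent change from the baseline-week mean, and report its own coefficients, confidence intervals and p<0.01 screen. Do not accept a predictor merely because the two analyses agree in direction. In a repeat of Simulation 2, percent change agreed in direction in every trial where point change falsely passed the screen (80/80, 193/193 and 626/626 at k = 1.1, 1.25 and 1.5), so that rule filters out nothing.

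The cost is a wording change on two forms, a sentence naming the scale, and one extra regression on data already collected. Percent change is noisier at low baseline values, though the entry requirement of average pain of at least 4 limits this. It also measures relative rather than absolute relief, so it supplements the main analysis and does not replace it.

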Beck depression Inventory: This self-report inventory consists of 21 multiple-choice questions and is widely used method to classify depression severity. It assesses for the presence of several symptoms related to depression, such as irritability, hopelessness and decreased cognitive performance. Physical symptoms such as weight loss and fatigue are also included. This instrument has been used previously to evaluate depression severity in patients with phantom limb pain [22], as well as in other chronic pain conditions [23, 24].

Beck anxiety Inventory: This self-report inventory consists of 21 multiple-choice questions about how the subject has been feeling in the last week, expressed as common symptoms of anxiety (such as numbness and tingling, sweating not due to heat, and fear of the worst happening). It is designed for an age range of 17–80 years old. Each question has the same set of four possible answer choices, which are arranged in columns and are answered by marking the appropriate one with a cross [25].

Mini Mental State examination (MMSE): This is a sensitive, valid and reliable 30-point questionnaire that is used extensively in clinical and research settings to measure cognitive impairment. This instrument will be used as a brief screening of cognitive abilities. It will be used as a baseline evaluation [26].

Quality of Life Assessment (Short version of SF-36): The short version of the SF-36 health survey is used as a measurement of quality of life. It provides a profile of functional health and well-being scores. It is also used as a psychometrical index of physical and mental health. This instrument is widely used as a quality of life assessment in patients after an amputation and those suffering from phantom limb pain [27-30].

Stroop test: In this task the subject is presented with names of colors written in the same color or in a different color, thus on the one hand the word names a color (red) and is written in another color (blue). In this task, the automatized behavior (reading) is in conflict with the desired response (naming the color). The Subject has to inhibit/suppress the automatic response of reading and naming the color the word is written in. The Stroop is one of the most commonly used tools for determining attentional problems, also used to assess executive function and working memory [31, 32]. Stroop test will be applied as a preliminary safety assessment of cognitive changes from baseline to post and follow-up visits.

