Side Effects Questionnaire for tDCS: At each stimulation session, subjects will complete a questionnaire to evaluate potential adverse effects of tDCS (tingling, burning sensation, headache, neck pain, mood alterations) on a 4-point scale (None, mild, moderate and severe). The subjects will be asked whether they have experienced any side effects in an open-ended manner and they will then be specifically asked about headache, neck pain, scalp pain, scalp burns, tingling, skin redness, sleepiness, trouble concentrating, and acute mood change. If any side effects are reported, the degree of relatedness to the intervention will be assessed on a 5-point scale. This type of adverse events questionnaire has been used frequently in our previous tDCS studies [23], including in patients with phantom limb pain [33].

VI. BIOSTATISTICAL ANALYSIS

Data forms and questionnaires will be coded in a standardized manner, and double-entered into our database. Digital measures/recordings will be similarly tracked in our database and regularly backed up. Analyses will be conducted using standard statistical software such as SAS and Matlab.

Sample size calculation:

This is an open label pilot study, we aim to recruit 50 participants with upper or lower, bilateral or unilateral amputation of any etiology that present chronic phantom limb pain at least in one of the amputated limbs. Given we are planning to build a multivariate regression analysis with up to 5 variables and considering 10 subjects per variable, a sample of 50 subjects would be appropriate for this exploratory analysis. The goal of this study is to provide data to generate further hypothesis regarding whether demographic and clinical factors influence treatment response as to be used for designing a randomized clinical trial (RCT). Therefore the goal of this study is not confirm a priori hypothesis but to provide critical data to design a RCT testing the effects of tDCS in this population of PLP.

Statistical Analysis

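### The side-effects questionnaire has no stated administration before treatment or in follow-up, so symptom reports lack a within-subject baseline and symptoms first appearing after session 5 are not solicited

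*Combined protocol and SAP*

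**What the plan says.** The design is an "open-label pilot study in which patients will receive active tDCS during 5 daily sessions" (Specific Aims). The four weeks start with a baseline week: "The first week, each patient will give daily reports of their pain using a VAS". Five treatment days come next, then "a final 2-week follow-up period without any treatment to examine the lasting effects of the therapy". The stimulation protocol agrees on the number of sessions: "Subjects will receive daily stimulation sessions with active anodal tDCS for 5 days".

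Under Description of Assessments, the Side Effects Questionnaire for tDCS is timed in one sentence: "At each stimulation session, subjects will complete a questionnaire to evaluate potential adverse effects of tDCS". Subjects first get an open question, and then "they will then be specifically asked about headache, neck pain, scalp pain, scalp burns, tingling, skin redness, sleepiness, trouble concentrating, and acute mood change". Any side effect reported is also rated for relatedness to the intervention on a 5-point scale.

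Two other instruments have a stated safety purpose:
- The Stroop entry says: "Stroop test will be applied as a preliminary safety assessment of cognitive changes from baseline to post and follow-up visits".
- The pain and medication diary is kept "To help monitor pain levels and medication use information, as well as safety". Its listed entries are phantom limb episodes, the intensity of the strongest one, phantom sensation, stump pain and medication. Medication is recorded daily to the end of the study.

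The Beck depression and anxiety inventories are listed without visit times; the only stated use is the depression score as an exclusion criterion. The Biostatistical Analysis section does not mention side effects.

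**The concern.** Several of the prompted symptoms are non-specific. People with chronic pain who may be on stable medication can have headache, neck pain, sleepiness, poor concentration or mood change without any stimulation. With no sham arm, the only available comparator is the subject's own state before the first session, and the plan does not record it for these symptoms. Whoever rates relatedness knows that every subject received active stimulation and has no earlier grade to compare with.

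At the other end, a symptom that develops after one of sessions 1 to 4 can be picked up by the form at the next session. After session 5 there is no next session, and no later prompt is stated.

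The sample size section says the study should supply data for designing a randomised trial. Tolerability is a natural input to that design, and a pre-treatment symptom grade cannot be recovered afterwards.

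**Working it through.** **The plan's own figure.** The only computed figure is the sample size: 5 variables × 10 subjects = 50. It reproduces, and this point does not depend on it. The documents give no side-effect rate, so there is no safety figure to check.

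**Coverage as stated.** Four weeks are 28 days.
- Baseline week: 0 of 7 days covered by the questionnaire.
- Treatment: 5 session days covered.
- Follow-up: 0 of 14 days covered.

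**Do the other instruments fill the gap?**
- The Stroop is given at baseline, post and follow-up visits, but covers cognition only.
- The diary runs through follow-up, but its listed items include none of headache, neck pain, scalp burns, sleepiness or mood.
- The Beck inventories may bear on mood, but have no stated timing.

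None gives a stated before-and-after reading of the questionnaire's symptom list.

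**How large could background reporting be?** Let *p* be the chance that a background symptom is present on a given session day, with no tDCS effect. The documents do not give *p*; 5%, 10% and 20% are assumed. Two patterns mark the ends of a plausible range:
- Fully persistent (the same subjects have it every day): share with at least one report = *p*.
- Independent days: share = 1 − (1 − *p*)^5.

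| Assumed *p* | Persistent | Independent days | Subjects of 50 |
|---|---|---|---|
| 5% | 5% | 1 − 0.95^5 = 22.6% | 2.5 to about 11 |
| 10% | 10% | 1 − 0.90^5 = 41.0% | 5 to about 20 |
| 20% | 20% | 1 − 0.80^5 = 67.2% | 10 to about 34 |

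These are raw reports, before the relatedness rating.

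**Would a baseline form help?** If symptoms are persistent, a baseline form identifies all of them. If days are independent, a form asking only about that day helps little. The share with a report in at least one session and none at baseline is (1 − *p*)[1 − (1 − *p*)^5]:
- 5%: 0.95 × 0.226 = 21%
- 10%: 0.90 × 0.410 = 37%
- 20%: 0.80 × 0.672 = 54%

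With recall over the 7 baseline days, assumed accurate, the first factor becomes (1 − *p*)^7:
- 5%: 0.698 × 0.226 = 16%
- 10%: 0.478 × 0.410 = 20%
- 20%: 0.210 × 0.672 = 14%

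So the recall period matters. It has a price: the share of subjects with some baseline symptom becomes 1 − (1 − *p*)^7 = 30%, 52% or 79%. In those subjects a true effect shows only as worsening, so all solicited symptoms need reporting as well.

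**The case against.** The strongest reply has five parts.

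- **Silence is not a prohibition.** The text never says the questionnaire is used at sessions only. This public version has no visit schedule, and its section numbers run II, IV, VI, so a schedule may exist elsewhere. This stands: the point is that no other administration is stated. If one exists, stating it meets the timing part of the point.
- **Background symptoms are not automatically counted as tDCS effects.** A reader might infer that they are. The relatedness rating exists to separate them, and the documents set no reporting rule that ignores it. This stands. What remains is that the rating is unblinded and has no baseline behind it.
- **Late effects are not necessarily missed.** A reader might infer this too. Follow-up visits take place, the diary has a stated safety purpose, and daily medication entries would show new drug use. Spontaneous reporting remains possible. This stands. What is absent is a stated structured prompt after session 5.
- **The higher percentages need assumed rates and independent days.** Recurrent symptoms tend to cluster within people, which moves the figures towards 5%, 10% or 20%. Under independence, a single same-day baseline form would still leave 21% to 54% labelled as emergent. This stands, and it is why the figures are given as a range and the fix uses a recall period.
- **Side-effect incidence is not an objective.** The aim is predictors of pain response, and no endpoint or model uses these data. This stands, and it limits the weight of the point. It does not remove the benefit of interpretable side-effect data from a study meant to inform a trial.

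**Conclusion.** The point holds in limited form. As written, the plan gives the prompted symptoms no pre-treatment reading and no solicited check after session 5, in a design with no control arm. Relatedness therefore has to be judged without an anchor, and raw counts mix background symptoms with any effect of stimulation by an unknown amount. The illustrative range runs from 5% to 23%, 10% to 41% and 20% to 67% of subjects for assumed daily rates of 5%, 10% and 20%. It rests on those assumed rates and on the two extreme dependence patterns, and says nothing about how reports would later be rated.

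The documents do not support saying that side-effect rates will be wrong by a given amount or that delayed effects will go undetected. The matter concerns the safety description alone; the predictor analysis and the sample size of 50 are unaffected. It is a cheap improvement worth making.

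**What to change.** - State in the questionnaire entry that the same form is also given at the baseline visit, before the first stimulation, with a defined recall period such as the baseline week so that intermittent symptoms are captured.
- Give it again at a follow-up visit after the day of session 5, asking about the time since the last session. If the post visit named in the Stroop entry falls on the day of session 5, use a later visit.
- In the analysis section, say that two summaries will be reported: all solicited symptoms, and those new or worse than the subject's baseline grade. Keep the relatedness rating alongside both.

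The cost is two more administrations of a short existing form per subject, or 2 × 50 = 100 forms in all, and slightly more data entry. Baseline and follow-up visits are already named for the Stroop test, so no extra visit should be needed.

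### The sample size of 50 is justified by at most five variables at 10 subjects each, but the planned model lists six covariates, which gives 8.3 per listed covariate

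*Combined protocol and SAP*

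**What the plan says.** The sample size paragraph of Section VI gives a rule of thumb as the numerical basis for recruiting 50: "multivariate regression analysis with up to 5 variables and considering 10 subjects per variable, a sample of 50 subjects would be appropriate". It uses no effect size, standard deviation, power or significance level. The same paragraph calls the analysis exploratory and intends it to inform the design of a later randomised trial.

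The analysis text for Aim 1 then proposes to "build a multivariate linear regression model in which the dependent variable will be the Visual Analogue Scale (VAS) for PLP using the following covariates". The covariates it names are "baseline pain (VAS), amputated limb (upper/lower), etiology of amputation (traumatic/ non traumatic), laterality of amputation (unilateral/bilateral), age, and gender", which is six. The Specific Aims give the same six, introduced by "We will examine whether the following predictors are associated with treatment response" and listed as "lower or upper limb, bilateral or unilateral and traumatic or non-traumatic amputation, baseline pain, age and gender by building a multivariate model".

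Two steps of model building follow. First: "The first step will be perform a univariate analysis for each one of our predictors using univariate linear regression". Then: "predictors associated with the outcome at a p level <0.01 will be used to build a multivariate linear regression using a forward stepwise model". Neither step sets a maximum number of terms.

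**The concern.** The count of variables used to size the study does not match the count in the model it is meant to size. Because subjects per variable is the only quantitative support for 50, a reader cannot tell what the figure of 10 describes: the six covariates examined, or the terms that remain after selection. On the first count the stated ratio is wrong as written. On the second it may hold, but nothing in the plan secures it.

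What is at stake is the accuracy of the justification. The results are to feed the design of a randomised trial, so the number of candidates examined per subject should be stated correctly.

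**Working it through.** **Inputs**
- Subjects recruited: 50 (Subject Selection, and the sample size paragraph).
- Variables assumed in sizing: at most 5 (sample size paragraph).
- Subjects per variable: 10 (sample size paragraph).
- Covariates named: 6 (Specific Aims, and Statistical Analysis for Aim 1). Limb, etiology and laterality are written as two-level factors. I take gender as one term, and age and baseline pain as linear, so each covariate costs one coefficient.

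**Step 1: the plan's own figure.** n = variables × subjects per variable = 5 × 10 = 50. This reproduces.

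**Step 2: the same rule on the listed covariates.** 6 × 10 = 60. With 50 recruited, the ratio is 50/6 = 8.3 per covariate.

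**Step 3: the rule on a five-term final model.** 50/5 = 10.0, which meets the rule exactly and with no margin. One subject not analysable gives 49/5 = 9.8.

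**Step 4: loss.** The documents give no allowance. As an assumption only, a loss of 5% to 20% leaves 47.5 to 40 subjects on average. That is 7.9 to 6.7 per listed covariate, or 9.5 to 8.0 per term in a five-term model.

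**Step 5: does the selection procedure hold the model to five terms?** By rule, no, because no cap is stated. The practical question is how strong the data must be for six terms to enter.
- With n = 50, two-sided p<0.01 on 48 degrees of freedom needs t = 2.682. That is |r| = t/√(t² + 48) = 0.361, or r² = 0.130.
- Assume all six covariates have the same correlation r with the outcome and a common pairwise correlation ρ. Then k terms explain R² = k·r²/(1 + (k − 1)ρ).
- The plan gives no entry level for the stepwise part, so two are shown. The table gives the smallest six-term R² at which all six pass the screen and every forward step enters.

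| ρ | Entry at p<0.05 | Entry at p<0.01 |
|---|---|---|
| 0 | 78% | 78% |
| 0.1 | 52% | 61% |
| 0.2 | 56% | 70% |
| 0.3 | 64% | 76% |
| 0.5 | 77% | 86% |

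The lowest value is about 49% (ρ near 0.12) for entry at p<0.05, and about 59% (ρ near 0.07) for entry at p<0.01. In this symmetric case a six-term model needs strong prediction. Unequal correlations were not examined, so the result does not extend to every pattern.

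**The case against.** The best defence is that a ceiling, rather than a fixed count, suits a model whose size is not yet known. On that reading the six covariates are candidates, the screen and stepwise step pick among them, and five bounds what is finally built. The limit also stands just before the analysis text, in the same section, so it need not be repeated there. The table above helps this case, since six terms would rarely survive under its assumptions.

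This reading is plausible, and it rules out calling the two places a flat contradiction. It does not settle the matter. The analysis text first describes the model as using all six named covariates, before any selection is mentioned. The selection rule has no cap and does not say what happens if six qualify. All six are tested against the outcome whatever is kept.

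A second defence would count five predictors plus baseline pain as an uncounted adjustment. The documents do not support that: the Specific Aims list baseline pain among the predictors to be examined, and the analysis text does not set it apart.

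On the other side, a reader might infer that the trial is too small, or that it must recruit 60. The documents do not support that either. The figure of 60 is only what the plan's rule of thumb gives for six variables. The plan makes no power claim and disclaims confirmatory intent.

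**Conclusion.** The point holds as a consistency error in the stated justification. The plan claims 10 subjects per variable, but on the six covariates it names the ratio is 8.3 before loss, and its own rule would give 60. The claim of 10 survives only if the limit of five applies to the final selected model and, at five terms, only if all 50 subjects are analysable. The first condition is unstated and unenforced, and the plan makes no allowance for failure of the second.

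The count of six assumes one coefficient per covariate. The finding does not depend on a six-term model being likely, and the symmetric calculation suggests that it is not. The issue is minor: the pilot is declared exploratory, and the aim, the covariates and the number recruited are unaffected.

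**What to change.** In the sample size paragraph, state that there are six candidate covariates and 50 subjects to be recruited, giving about 8.3 subjects per candidate before loss. Say plainly that this falls below 10 per variable and is accepted because the analysis is exploratory. That sentence is needed, because without it the new ratio would leave 50 with no stated basis.

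Alternatively, if a five-term final model was intended, keep the present ratio and add the limit to the Aim 1 analysis text, with the rule that forward selection stops at five terms. This covers the case where a sixth would qualify.

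Either change is wording only. No covariate is dropped and no patients are added. The cost of the first is a less favourable ratio that openly misses the plan's own rule. The second keeps the ratio of 10, but only for the final model and with no margin for loss.
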